If determined a follow up call would provide valuable feedback on VA-INTERACT usage in the VA CLC setting based on the above criteria, the exit survey team will email the designated champion requesting a time to speak over the phone to expand or clarify some of their responses. Through email, the exit survey team member and champion will determine a time to schedule this call. The exit survey member will call the champion at the designated time. If they are unavailable at this time, a message will be left regarding a time to reschedule. Also an email requesting at time to reschedule will be sent, this email will remind the champion that their participation is voluntary. If they no longer wish to participate, they can reply to the email letting the exit survey member know and no future contact will be made. If no response is received from the champion a second email will be sent a week later to try to reschedule the call. This will be the final attempt and it will be noted in the email that this is the final contact. Only if a response from the champion occurs will any further contact be made to schedule this call.

The information gathered will be entered into their survey responses to those narrative questions being followed up on from that champion.

The exit survey research team will compile the completed interviews, stripping them of the CLC and Champion name, replacing with an ID. Only the exit survey research team will have access to connect the champion or CLC with their interview responses. The exit survey staff will keep the coded list of champions' names and IDs and their responses on a secure server within their local VA system. The local VA exit survey team will be responsible for analyzing and providing the outcomes from these interviews to the rest of the research team

Aim #3: To conduct a quantitative and qualitative evaluation of the implementation of INTERACT in order to characterize the fidelity with which CLCs in the intervention participated in training, engaged in regular conference calls, undertook root cause analyses identifying why hospitalizations occurred and used the other tools in which they were trained.

The proposed documentation of the implementation of the INTERACT intervention will have both a quantitative as well as a qualitative component. We will rely upon the data recorded as part of the documentation of the intervention process to characterize the extent of adherence to INTERACT over the course of the training period and across the participating CLC sites. Each site will be characterized in terms of the following: percentage of direct care staff who initiated and completed the on-line training; the percentage of training calls attended by the Champions; the proportion of hospitalizations for which a root cause analysis was completed by the nursing staff; and the number of SBAR and Stop & Watch tools reported on by the Champions per week. To document changes in the intervention from the beginning of the training period to the end of the monitoring period, we will calculate some metrics on a monthly basis to share with the CLC, allowing for the likelihood that the level of adherence of the intervention will change over time, presumably rising throughout the 6 month training period and

beginning to decline during the monitoring period.

The qualitative component of the intervention will be undertaken throughout the monitoring period during the numerous regularly scheduled calls with CLC representatives. An audit trail of anecdotal feedback derived during these calls will be kept in a restricted folder on the SharePoint which only Providence Research staff on this project will have access to.

We are aware the data may be impressionistic and may not accurately reflect the variation in how the intervention was implemented over the duration of the project. However, having information on the utility of the INTERACT tools, how they were used in practice, and how that use changed from the start of the active 6 month training period compared to the 12 month monitoring period will be very valuable in ascertaining fidelity to INTERACT protocols and uptake of intervention. This may help explain possible differential results between facilities.

Aim #4: *To test the effect of the INTERACT intervention on the rate of reduction in hospitalizations from intervention CLCs as compared to the matched control CLCs and to determine via a formalized structured implicit review (SIR) process whether the intervention was associated with a reduction in “avoidable” hospitalizations and that it did not lead to negative outcomes like mortality and ADL decline.*

We will test the effect of INTERACT on the rate of hospitalization from CLCs taking advantage of *both* the paired control CLCs as well as the differences in the hospitalization rates among intervention facilities before and after the implementation of the intervention. The primary outcome variable is the monthly rate of hospitalization, which, after adjusting for seasonality and trends in the rate over several years prior to the intervention, is compared to the rate of the paired comparison CLC. To allow for regional differences in seasonality, separate ARIMA models will be run for each CLC and then we will use the monthly difference between the observed to the expected CLC hospitalization rate value to compare between the two matched CLCs, aggregating these differences overall pairs. Technically, the average monthly rate of hospitalization before the intervention will be compared to the average monthly rate after and the difference between these two rates will be compared to the differences in the rates of the comparison facilities, using a standard *difference in difference* design.

A similar approach will be used with the person level, risk adjusted hospitalization rates for short and long stay residents calibrated as an annualized rate and there will be fewer facility years than were facility months under the approach described above. The unit of analysis will be the CLC resident but the standard errors will be clustered at the facility level.

Using the results of the Structured Implicit Review process, we will determine the percent of hospital transfers rated as avoidable through better quality of preventive care and early change recognition and the percent rated as inappropriate because the Veteran’s condition could have been safely managed in an average VA CLC. We will compare the percentage hospitalized before the implementation to that after implementation. The sample size of 326 hospitalization records, 163 pre and 163 post-INTERACT, is based upon the assumption that the pre-intervention rate of potentially avoidable hospitalizations will be 40%. For the overall project, we are hypothesizing that there will be a 20% reduction in hospitalizations. Logically, the reductions in hospitalizations will come primarily from the "avoidable" type (otherwise we have a causal inconsistency). Thus, if 40 of 100 hospitalizations pre INTERACT are avoidable and all of the 20% reduction in hospitalizations (20 of 100) will come from among those that are avoidable, we expect a 50% reduction in the rate of avoidable hospitalizations. So, if the pre rate is 40% and the post rate is 20%, using a one tailed test at the alpha .05 level, we need about 100 records

before and 100 after to achieve a power of .90. In the event that some "unavoidable" hospitalizations are really avoided due to the intervention, we increase the sample size to 163 per time period.

Finally, we will test for unintended consequences by examining changes in the rates of overall mortality and in the rate of decline in the late loss ADLs, as measured by the MDS 3.0 nursing home resident assessment, which is done upon admission, periodically thereafter and upon discharge.[45]

Random selection of records with a transfer: A total of 326 medical records with a transfer to the hospital and across the eight intervention CLC sites will be reviewed, 163 pre-INTERACT intervention and 163 post-intervention.

The 163 pre-INTERACT records will be selected from a list of transfers that occurred during the 18 months prior to INTERACT being introduced to the CLCs. This list will be compiled by the study programmer/analysts who will pull it from current CDW data and MDS data. Once the list is generated, random selection will occur to obtain 163 records pre-intervention.

A second list of transfers will be generated across the intervention CLCs for the post-intervention period and a random selection of 163 of these transfers will also be selected for review.

Once each set of records is selected, the 326 records will be combined and randomized. The randomized list will be randomly divided amongst the reviewers (and include a randomized portion of the records to be used for training on how to complete the SIR).

Reviewer Recruitment and training: Up to 17 physicians or other clinical experts from within the VA and with a geriatric background will be recruited by [name] and her team from LAVAMC. These individuals will be added as study team members and will be required to complete a two-day training (in-person or web based), sign confidentiality and privacy agreement, be provided access through CAPRI (Compensation and Pension Record Interchange) /VistaWeb to the 8 intervention sites through an amendment to the DART DUA for this purpose, provided access to a secure restricted folder within the Providence VA Research Server and access to their secure SharePoint.

To avoid the use of INTERACT influencing the reviewers' structured implicit review we will NOT recruit anyone from our existing CLC intervention sites.

After the reviewers complete their assigned chart reviews they will participate in a debriefing with the LA team, notifying them about the use of INTERACT as the QI intervention and the impact their reviews will have on determining INTERACT's effectiveness at preventing 'avoidable' hospitalizations from occurring within the CLCs.

The reviewers will be trained to use CAPRI/VistaWeb to complete the chart reviews. CAPRI/VistaWeb provides a standardized, user-friendly method to access the charts for review within VA.

Structured Implicit Review (SIR) Procedure: Each reviewer will be randomly assigned an equal percent of the 326 charts to review based on the number of reviewers. The charts will be randomly assigned, from across the intervention sites to the reviewers. The reviewers will not be provided any specific information about the intervention conducted using INTERACT or any indication of whether it was a pre or post intervention chart.

The reviewers' will then complete their review of the charts using the SIR Instruction Manual and Guide (See Appendix 7, Structure Implicit Review Instructions and Guide). They will utilize access to a

restricted folder within the Providence VA Research Server and PKI encryption by email for this purpose throughout the process to do the reviews and share information with the research team, from Providence and LAVMC related to assistance with the SIR process.

The reviewers will complete each review using the SIR Instructions and Form (appendix 7). They will save each review to the secure designated restricted folder. If they choose to hand write their responses, they will scan the original review in and save on the secure restricted designated folder or send encrypted (PKI) to the project coordinator in Providence to be stored on the secure restricted folder within the Secure Providence VA Research Server. The original hand written copies will be stored locally in a designated locked location by the reviewer for the specified time frame noted in RSC-10.

While the reviewer will have access to complete medical records, only specific identifiable information from any medical record will be shared with the research staff (from Providence and LAVMC) to assist them in making sure they are accessing the correct record prior to their reviews. That information would include the Veterans name, Date of birth, last four of SSN, treatment dates being reviewed and the information contained in the Review Form (appendix 7).

REDCap may be used to input the reviews for analysis. The reviews would be input by Providence VA research team members, stripped of any identifying information and used to confirm the hypothesis that a reduction in avoidable hospitalizations was accomplished by the use of the INTERACT intervention, specifically the use of the SBAR change in condition progress note within CPRS. Review by the local privacy officer and local ISO confirms that the use of REDCap for the requested data is acceptable and within the guidelines of use.

REDCap is a secure data storage method. We will use this data storage option because it provides: 1) an intuitive interface for validated data entry; 2) audit trails for tracking data manipulation and export procedures; 3) automated export procedures for seamless data downloads to common statistical packages; and 4) procedures for importing data from external sources.

Aim #5: *To conduct a Budget Impact Analysis (BIA) of the INTERACT program from a VA perspective, using the 2-year study follow-up period as the time horizon. Given the important public policy implications for Medicare, we will conduct a secondary BIA from the perspective of the entire Federal Government. The purpose of the BIA is to provide VA managers with the budget impact information they need to manage the start-up and implementation of the program if this project demonstrates that INTERACT works in VA. Preliminary non-VA studies have found INTERACT to save more than 15 times the cost of the intervention. Thus, even if INTERACT is less effective in VA, it still should yield significant savings.*

The BIA will be driven by the other Aims' estimates of the VA effectiveness of INTERACT. As part of the intervention, we will carefully track both the start-up and on-going labor associated with INTERACT. Actual VA labor costs will be used to value this time. The cost savings of the program are not directly observed as they are the hospitalizations that INTERACT prevents, and thus must be estimated. We will obtain data on all VA and Medicare hospitalizations and other types of care. VA costs will be obtained from the DSS fee-basis files, and the Medicare reimbursement will be used as the estimated costs of non-VA care. The first analysis will be to compare the hospitalization costs between the intervention and control sites, including looking for offset effects for other types of care (reduced hospitalizations being partially offset by higher costs for other types of care, including higher costs in the CLC).

We will conduct a full sensitivity analysis of the estimated savings, of how quickly they accrue, and of potential off-setting cost increases. The extent of the savings will be driven by how the intervention affects both the rate of hospitalization, and of the types of hospitalizations (costs vary significantly by the types of conditions treated). Another concern is that the DSS cost estimates include fully allocated overhead costs. The details in the DSS cost data will be used to provide information about how the potential cost savings are distributed across variable direct care costs (e.g., supplies and nursing labor), costs that can only be changed over time (e.g., reallocation of space to other types of care), and allocated overhead costs that will not change with the program.

Statistical Considerations:

We estimate our power to detect an expected decrease in hospitalization rate over a 24 month period using simulation analysis, over different scenarios with different sample sizes (# of CLCs), to predict the expected power of our pair matched experiment. Previous research reveals that a Auto-Regressive Moving Average (ARIMA) model characterizes hospitalization rate trends with high accuracy. In our simulations analysis we assume that each CLC’s rate follows an ARMA(2,2) model of the following form:

$$Y_t = c + \epsilon_t + \sum_{i=1}^2 \rho_i Y_{t-i} + \sum_{i=1}^2 \theta_i \epsilon_{t-i}$$
, where ρ_i the correlation of the current to the previous i months, θ_i is the parameter that describe the effect of the error at time $t-1$ on the current hospitalization rate, ϵ_t is normal random with mean zero and standard deviation of σ_ϵ and c is the overall expected hospitalization rate. The simulation analysis included 5 parameters: 1) the sample size in the treatment group; 2) an increase/decrease in the hospitalization rate variance σ_ϵ (F); 3) the size of the effect (c); 4) the accuracy of the decrease $\sigma_{c.}$; and, 5) the variability of ρ_i , θ_i of the nursing home that received treatment from the matched nursing home that received control σ_d . For each configuration of the five parameters, the following algorithm was repeated for 100 times: 1. a sample of n yearly hospitalization rates was chosen from currently observed empirical hospitalization rates and assigned to treatment and control CLCs; 2. sample ρ_i 's, θ_i 's from the above ARMA(2,2) model randomly generated for each of n treatment CLCs; 3. for each i treated nursing home we perturbed the ρ_i 's, θ_i 's by a factor of σ_d , and assigned them to the pair matched control CLC; 4. generate $2n$ ARMA processes using the ρ_i 's, θ_i 's generated in step 2 and 3, and the variance σ_ϵ/F ; 5. decrease the hospitalization rate in the treated group gradually by 5c% to 20c% over 24 months + random deviation of σ_c ; 6. calculate the monthly differences between the treated nursing home hospitalization rate to its matched control, and average across 24 months (τ_j) and calculate the standard error σ_{τ_j} ; and finally, 7. use the average and variance

$$\frac{\sum_{j=1}^J \frac{\tau_j}{\sigma_{\tau_j}}}{\sum_{j=1}^J \frac{1}{\sigma_{\tau_j}}} \text{ and its pooled variance } \left(\sum_{j=1}^J \frac{1}{\sigma_{\tau_j}^2} \right)^{-1}$$

calculated in 6 to obtain overall weighted average and its pooled variance. To find the factors with the largest effect on power, we calculated the MSE of all the main effects and their interactions. The F, n and c are factors that capture 93% of the variability in the data. Figure 1 shows how the # of CLCs and F (variance of hospitalization rate) affect the power of our analysis. . Even if the monthly reduction in hospital rate will be as low as 10%, using 8 treatment CLCs will result in .77% power.

Figure 4: Power Estimates, Number of CLC’s by Effect Size and Variance in Monthly Hospitalization Rates

Effect	20% Reduction in Hosp. Rate	10% Reduction in Hosp. Rate
--------	-----------------------------	-----------------------------

size										
# CLCs	6	7	8	9	10	6	7	8	9	10
.5	1	1	1	1	1	.99	1	1	1	1
1.0	.98	.99	.99	1	1	.7	.74	.77	.81	.84

Preliminary Studies:

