Based upon merged VIREC and Medicare inpatient and outpatient data and CLC nurse staffing and other organizational data, we will match CLCs in terms of hospitalization rate, proximity to their VAMC hospital, admissions per bed and the mix of short and long stay CLC Veterans they serve. Up to 15 pairs of CLCs will be identified and from each pair one CLC will be randomly selected and approached about implementing the INTERACT program. We expect a minimum of 8 of the facilities approached to accept, adopt and implement the program over the 6 month training period and the additional 24 month implementation and data collection period (encompassing: a 12 month monitoring and data collection period to review the results of the intervention, followed by 12 months of indirect data monitoring). Both members of the CLC matched pairs will be dropped from the study if the CLC that is randomly selected to be offered the INTERACT program declines to participate. During the 6 month training period and the 12 month active monitoring and data collection period, extensive process measures, such as CLC staff participation in online training and support conference calls, will be gathered for use in both the implementation analyses as well as the Budget Impact Analysis (BIA). Additionally, quality improvement tools applied by staff to examine the characteristics and “avoidability” of hospitalizations during the 6 month training and 12 month active monitoring period will be assembled and coded. There will be no contact with pair matched control CLC since outcome data on their hospitalization rates will come exclusively from existing data. Changes in the case-mix composition and seasonally adjusted hospitalization rates for both the intervention and control CLC in each pair will be examined by comparing data from the two years prior to the introduction of INTERACT with data from the two years after the introduction of INTERACT.

Data Sources: To estimate the impact of the INTERACT on the rate of hospitalization from CLCs a variety of administrative data will be used. Our strategy for merging data is described below.

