Once CLCs are matched, the randomly selected CLC will be approached to solicit their participation with the strong endorsement of GEC leadership. We will approach the randomly selected experimental CLCs until up to 15 have agreed. If a CLC declines to participate, both members of the pair of matched CLCs will be dropped from consideration. The matched “control” case of those CLCs that agree to participate in the INTERACT program will not be approached. The “control” status of a CLC will be known to no one outside of the project research team and will not be divulged in any project description or publication.

Patient Selection: We do not anticipate excluding any Veterans in CLCs from the population to be included in the outcome analyses. The CLC is the unit of random assignment, meaning the intervention changes the skills of CLC staff. For each CLC agreeing to adopt the INTERACT program, it will be as if the CLC is introducing a focused quality improvement program to their staff. As such, no individual patient consent will be requested. We will separately examine hospitalization rates of Veterans classified as long stay or short stay based upon the pattern of recent admission and discharge data, but this will be regardless of their clinical condition or diagnoses.

Outcome Measures: The primary outcome (on which our statistical power estimates were based) will be the **overall hospitalization rate** calculated as the number of admissions to hospital from

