the CLC in a month per person year at risk of hospitalization in that month. This measure has been constructed per CLC using VHA-Medicare merged data from 2004 and afterwards obtained under [name] current HSR&D IIR. The measure will be constructed covering the period from at least the 24 months preceding the introduction of the INTERACT program until 24 months after the introduction of the INTERACT program. Since hospitalization rates vary substantially during flu season, we have fit an ARIMA model to reduce the heterogeneity of variance in this monthly measure of hospitalization, thereby reducing the heterogeneity of residual variance. An ARIMA model will be fit for each CLC in the study, then using the monthly difference between the observed to the expected value to compare between any two matched CLCs over time. The dependent measure is a facility aggregate which we will risk adjust using indirect standardization by stratifying the per CLC month measure separately for long stay and short stay person months at risk of hospitalization. [See the Statistical Considerations section below for a detailed presentation of the ARIMA model.]

[figure not shown]

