Documenting Intervention Fidelity: The process of implementing and remaining true to the fidelity of INTERACT will be documented in a uniform manner across all intervention CLCs using the web based training, documentation of attendance on conference calls, qualitative notes from site visits, and from fielding trouble shooting calls. Specific items of interest that will be examined and reported will include: a change in the Champions; the proportion of staff who complete the web-based training; the number of Stop and Watch Early Warning Tools used; the number of SBAR Progress Notes completed relative to the number of hospitalizations per month; and any increase in the number of CLC residents with advance care directives. Variation between CLCs participating in the INTERACT intervention will be one of the foci of an implementation report. We will also document the association between a global assessment of “adherence” to the INTERACT intervention and the degree of reduction in the actual rate of hospitalization from CLC by CLC Veteran. Counts of contacts, calls and numbers of forms filed will be differentiated between the first 6 month period and the second 12 month monitoring and data collection period.

In order to evaluate intervention fidelity, we will use data on the number of CLC staff who complete INTERACT training, participate on teleconferences, and obtain information from project Champions during regularly scheduled calls on the use of specific INTERACT tools (Stop and Watch Early Warning Tool, SBAR, Quality Improvement Tools, and Advance Care Planning Tracking). The Project Coordinator will track receipt of data and will contact project Champions with reminders and follow-ups if data is not submitted.

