CLC agreement to participate: Up to 15 CLCs will be identified as potential participants in the INTERACT intervention program based on a pair matching system and random selection of one CLC from each pair. If the selected CLC does not agree to participate the pair will be dropped and we will go back to the remaining list of potential pair matches and select another site until up to 15 have agreed to participate or we have contacted all eligible sites.

The formal training at each CLC is scheduled to occur over a 6 month period followed by 12-18 additional months of observation. A minimum level of participation in the training is required to

ascertain that the intervention has been embraced by the CLC staff. The Providence research staff will monitor the CLCs' participation in the intervention. If a CLC is doing poorly and the Champions seem to be unable to engage and motivate the staff, we may drop the site or try to recruit an additional Champion(s). This is one of the reasons for matching extra pairs of CLCs. One of the strengths of the pair matched design is that if one of the intervention CLCs is dropped we can readily drop the matched control site without having to worry about unbalancing the design.

Each CLC will follow the procedure below to become an active participating CLC in the INTERACT intervention. Selected CLCs will be contacted with a letter from the PI, [name], Co-PI [name], MPH, INTERACT Developer, [name], and GEC leadership containing introductory material, describing the INTERACT training program being proposed. After the letter, follow up contact will be made with each CLC to determine participation. Sites who agree to participate will be asked to sign a Research Study Agreement (See Appendix # 3, Research Study Agreement).

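### Matched pairs can leave the study after random selection because of the selected CLC's refusal or poor engagement, and no analysis of all approached pairs is planned

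*Combined protocol and SAP*

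**What the plan says.** **Refusal.** One CLC of each matched pair is chosen at random and then invited. CLC Selection, Matching and Random Assignment states: "If a CLC declines to participate, both members of the pair of matched CLCs will be dropped from consideration". Study Procedures (Overview), The INTERACT Intervention and Aim #2B repeat the rule. Aim #2B adds replacement: "we will go back to the remaining list of potential pair matches and select another site until up to 15 have agreed".

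**Poor engagement.** Aim #2B requires a minimum level of participation but gives no figure. Where staff are not engaged, the team may either drop the site or recruit more Champions. It presents pair deletion as a strength of the design: "we can readily drop the matched control site without having to worry about unbalancing the design".

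**Controls.** The Overview states: "There will be no contact with pair matched control CLC since outcome data on their hospitalization rates will come exclusively from existing data".

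**Analysis.** Outcome Measures states: "An ARIMA model will be fit for each CLC in the study". Aim #4 compares observed-minus-expected monthly rates within pairs by difference in difference. Two fidelity analyses bear on engagement. Under Documenting Intervention Fidelity, "Variation between CLCs participating in the INTERACT intervention will be one of the foci of an implementation report", and adherence will be related to the fall in hospitalization. Aim #3 says of its adherence data: "This may help explain possible differential results between facilities". Both concern participating sites only.

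**Limitations.** The third limitation assumes that CLCs offered the program will want it. It does not say what follows if they do not.

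**The concern.** Randomisation makes the two members of a pair exchangeable when one is selected. Whether the pair then stays depends only on how the selected member behaves. The control is never asked, so its willingness is neither observed nor used. Among retained pairs, every intervention CLC has accepted and stayed engaged, while the controls include some that would have refused or engaged poorly. If willing or engageable CLCs would have changed differently over the follow-up anyway, that difference enters the treatment contrast.

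Removal for poor engagement is the more serious route, for three reasons:

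- It happens after exposure to the program and has no numeric criterion.
- Under Aim #2B the Providence research staff monitor participation. Under Data Assurances the same staff track hospitalization and mortality data for the paired facilities. Removal could therefore follow results.
- The Introduction reports that engagement tracked outcome in the earlier evaluation: a 24% reduction in engaged homes against 6% in homes rated not engaged.

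At stake is whether the result can be read as a matched-pair randomised comparison, and whether a reader could check that reading.

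**Working it through.** **1. What the planned safeguards cover.** Matching on five years of rates, leadership review before approach, the staffing comparison and the ARIMA-adjusted difference in difference address differences visible before introduction, or help interpretation. None removes a later divergence linked to willingness. The Overview drops declining pairs from the study, so nothing commits the team to modelling them.

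**2. Refusal bias.** Let q be the share of approached CLCs that decline, r the share of pairs whose members share the same willingness, and g the gap in untreated change between willing and unwilling CLCs. Retained intervention CLCs are all willing. A share q(1 − r) of retained controls is not. So

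bias = q × (1 − r) × g.

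The documents do not give g. I assume 0 to 10 points. For q, The INTERACT Intervention provides for up to 4 refusals among 17 pairs. The Overview and the selection section allow as few as 8 sites from up to 15 pairs. Treating that whole shortfall as refusals gives 7/15, and the same minimum from 17 pairs gives 9/17.

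| q | g = 10, r = 0 | g = 10, r = .5 | g = 5, r = 0 |
|---|---|---|---|
| 4/17 = .235 | 2.35 | 1.18 | 1.18 |
| 7/15 = .467 | 4.67 | 2.33 | 2.33 |
| 9/17 = .529 | 5.29 | 2.65 | 2.65 |

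The bias is zero if g = 0, if r = 1 or if none decline. A simulation of 200,000 pairs with no treatment effect, g = 10 and q = 4/17 gave retained-pairs differences of 2.37 (r = 0) and 1.17 (r = .5) in absolute size. Over all approached pairs the difference was within about 0.02 of zero.

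**3. Standard error for scale.** The plan's ARMA(2,2) simulation cannot be rerun, because its coefficients, error variance and alpha are not given. I calibrate to its stated power of .77 for a 10% reduction with 8 treatment CLCs. The assumptions are a constant 10-point effect, equal variance across pairs and a two-sided .05 test:

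SE(8) = 10 / (1.960 + 0.739) = 3.71 points; SE(n) = 3.71 × √(8/n); SE(13) = 2.91.

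Check against the plan's power table at 6, 7, 9 and 10 CLCs: this gives .65, .71, .82 and .85, where the plan has .70, .74, .81 and .84. The gaps are roughly within simulation error, since 100 replicates give a standard error of about .04.

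The upper values compare as follows:

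- 13 retained: 2.35 / 2.91 = 0.81 standard errors. With no treatment effect, a nominal 5% two-sided test would reject about 13% of the time.
- 8 retained of 15: 4.67 / 3.71 = 1.26 standard errors, with rejection about 24% of the time.

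These ratios may be too low. Statistical Considerations phases the reduction in over 24 months and then averages. If the mean effect behind the 10% label were 5 points (an assumption), SE(13) would be 5 / 2.699 × √(8/13) = 1.45, and 2.35 would exceed it.

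**4. Power of an all-approached-pairs analysis.** Assume no effect in decliners and dropped sites. The effect is multiplied by retained/approached, and the SE uses all approached pairs.

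| Retained/approached | Diluted 10% effect | SE | Power, 10% | Power, 20% |
|---|---|---|---|---|
| 13/17 | 7.65 | 2.54 | .85 | above .99 |
| 8/15 | 5.33 | 2.71 | .50 | .98 |
| 8/17 | 4.71 | 2.54 | .46 | .96 |

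For comparison, the retained pairs alone have power .93 (13 pairs) and .77 (8 pairs) for a 10% effect. A one-sided .05 test, recalibrated to SE(8) = 4.20, gives .84, .54 and .50 for the 10% effect, and above .99, .97 and .95 for the 20% effect.

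**The case against.** The retained-pairs analysis is defensible. Impact of Findings states its expectation for CLCs that fully implement the program, and that analysis targets them. Leadership endorsement may keep refusals low, and the Limitations state the interest assumption under which refusal bias vanishes. The gap g has no source in the documents, and the bias range includes zero. Dropping a site is only one option in Aim #2B. The all-pairs analysis has roughly even power for a 10% effect if only 8 sites are retained. All of this stands. It argues for keeping the planned analysis and making the new one supplementary, not for leaving the selection unexamined.

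Four stronger readings are tempting, and the documents do not support them:

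- **The result is biased in the program's favour.** Neither the sign nor the size of the bias can be derived from the documents.
- **The 24% and 6% figures measure the bias.** Both groups were given the program and were not randomised to engagement. The contrast shows association, not a difference in untreated change.
- **Sites are dropped because of their results.** The text permits removal for poor engagement by staff who also track rates. It does not say that rates drive removal.
- **The bias is always below one standard error.** That holds at 4 of 17 declining under a constant-effect calibration. It fails at 7 of 15, and may fail at 4 of 17 once the phased effect is allowed for.

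**Conclusion.** The concern holds. Pairs leave after random selection on one member's behaviour, so the retained comparison is not fully protected by randomisation, and the plan contains no analysis that would test this. Aim #2B's reassurance about balance is right for pair counts and wrong if read as covering willingness or engagement.

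Under an assumed gap of 0 to 10 points and independent willingness within pairs, refusal bias is 0 to 2.4 points at 4 of 17 declining and 0 to 4.7 at 7 of 15 (5.3 at 9 of 17). It halves if half the pairs share willingness. The upper values at 4 of 17 and 7 of 15 lie below and above one standard error respectively, on a calibration that may overstate the standard error. Engagement drops are not quantified. The trial is not invalidated. Confidence is medium, because the bias is possible but not shown, and appendices and some text were not available to check.

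**What to change.** 1. Keep every approached pair in the data extract, including decliners and sites dropped for poor engagement, with a log of approach, refusal and drop. Give decliners an index date by a rule fixed before outcome analysis, for example the training start of the cohort nearest the approach date.
2. Add a supplementary difference-in-difference of all approached pairs as randomised, beside the retained-pairs analysis. Report the numbers and baseline rates of pairs approached, declined and dropped.
3. State under Limitations that the retained-pairs result is subject to post-randomisation selection. Qualify Aim #2B to say that pair deletion preserves pair counts only.
4. Reconcile the site and pair counts, which set the denominator: 8 to 15 (specific aim 2), up to 15 (Overview, selection section, Aim #2B), 17 (The INTERACT Intervention), 8 to 10 (Tampa data handling plan), eight (record selection and reviewer access under Aim #4) and ten rows (Quarterly Monitoring Report).

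**Cost.** No site contact is needed. Outcomes come from existing data, and Risks to Subjects puts data for all Veterans in long term care from 2008 through 2017 in scope. The protocol version is dated June 2017 and the project chart schedules training for 4/15 to 8/15, so the log may have to be rebuilt from records. The all-pairs estimate answers a different question, the effect of offering the program. Its power for a 10% effect is lower, which is why it should not replace the planned analysis. The loss is smaller if dropped sites keep part of the effect.
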